#### Feasibility and timeline

The project will be carried out at the four Danish liver surgery centers (Rigshospitalet, Odense, Århus and Aalborg). Office space and facilities will be provided. The project group includes experienced researchers and surgeons specialized in liver surgery.

In 2019 and 2020, approximately 45-50 patients each year with liver malignancies were treated solely with ablation during open surgery in Rigshospitalet. The majority of these patients may be included in the present study. Approximately half of the procedure in Denmark are performed at Rigshospitalet

with the remaining distributed between the others centers in Odense, Århus and Aalborg. Thus, we expect that all patients for this study can be recruited in approximately 1.5 years (see sample-size calculation). The procedures will be performed by experienced liver surgeons to maintain the technical skills required.

The project will form the basis of a PhD project and results will be published in international peer-reviewed scientific journals. The PhD-student will handle inclusion at Rigshospitalet, follow-up, data collection, statistical analyses, and writing of three papers. A PhD-student will be hired through the job portal of Copenhagen University and sundhedsjobs.dk. Based on interviews, we will hire the best qualified candidate. The study group members in Odense, Århus and Aalborg will handle inclusion of patients and perform the procedures in their own center. The study has been funded from The Danish Cancer Society “Knæk Cancer”, which covers three year salary for a PhD-student and a 20% research position designated to the primary investigator.

#### 4. Statistical considerations

We will use descriptive statistics and the dataset will be described with frequencies and percentages for categorical variables and means or medians for continuous variables. Primary outcome and rates of secondary dichotomous outcomes will be compared between the groups using Fischer's exact test. Mean VAS score will be compared using Mann-Whitney U-test. To determine risk factors affecting ablation response, logistic regressions will be used in both univariable and multivariable analyses. The EORTC Quality of Life questionnaire is designed to measure cancer patients' social, physical, and psychological functions. Quality of life will be reported using the summary score with the intention of comparing patients treated with either laparoscopic or open ablation. Mann-Whitney U-test will be used to assess differences in the summary scores. Analyses will be performed both on intention-to-treat and per protocol levels. The level of statistical significance will be set to  $p < 0.05$ . All statistical analyses will be performed using R, version 4.0.3.

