## 1. Title

# **Laparoscopic versus open ablation of liver malignancies: a randomized, controlled multicenter trial**

## 2. Aims

We will conduct a randomized study to compare laparoscopic ablation for liver tumors with the standard care (open ablation) with the hypothesis to reduce complications and maintain similar treatment success rate. We will

- Investigate differences in complications (primary outcome), length of hospital stay and mortality between laparoscopic and open ablation.
- Investigate differences in success rate (complete ablation response) between laparoscopic and open ablation.
- Investigate differences in quality of life between laparoscopic ablation and open ablation and explore how patients with liver tumors experience ablation of a liver tumor.

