Ablation therapy is often guided by real-time ultrasound and can be performed either percutaneously, by laparoscopy or by laparotomy (open). Percutaneous ablation is the least invasive approach and is gold standard for the treatment of HCC and liver metastases when possible. However, some tumors may not be accessible percutaneously due to risk of injury to adjacent organs or due to insufficient visualization of the tumor. Ablation during open surgery allows treatment of tumors in locations difficult to reach percutaneously. At present, patients who cannot be treated percutaneously are offered open ablation in most centers. However, open surgery may be associated with a higher risk of complications which may be devastating for frail patients and patients with impaired liver function. More than 80% of patients diagnosed with HCC have preexisting cirrhosis, and these patients are at a higher risk of complications and have a higher postprocedural mortality due to the impaired liver function and portal hypertension. Therefore, a minimally invasive approach is considered especially relevant in these high-risk patients. Laparoscopic ablation is less invasive with a presumed lower complication rate than the open approach, however, offers some of the same advantages needed for tumors in locations not favorable for percutaneous ablation.

Success of the procedure is demonstrated by a complete ablation of the macroscopic tumor assessed by contrast-enhanced ultrasound or CT one month after procedure. Previous studies reported a complete ablation achieved in 94-100% of patients treated with ablation with no significant difference between percutaneous, laparoscopic, or open approach. However, no comparative study has been performed.

A study from our department found complications in 45% of open ablations based on the Clavien Dindo Classification which was comparable to that of patients undergoing liver resection. An external study found comparable results of 39.5%. In contrast, the complication rate after

percutaneous ablation is as low as 5% and the literature suggests that laparoscopic approach have similar low complication rates.

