## 3. Method

The study is a randomized, controlled, multicenter study in patients with liver malignancies treated at the four Danish liver surgery centers (Rigshospitalet, Odense, Århus and Aalborg). Patients with one or more liver tumor suitable for ablation as primary treatment, but not amenable for percutaneous ablation will be randomized between laparoscopic and open ablation. Opaque envelopes with patient numbers containing the randomization sequence will be opened after informed consent has been obtained. We plan to include 80 patients with 40 patients per arm. Patients will be randomized 1:1 (see below). Randomization will be stratified on center level to ensure comparable populations between the groups within each center.

Due to perioperative findings, the treatment to which the patient is randomized to may be considered not feasible or inappropriate, e.g. due to insufficient visualisation of tumor or findings that warrant a different treatment strategy. In these cases, the treatment strategy is based on the surgeons preferences. In laparoscopic cases, a minimally invasive approach should be maintained if possible, e.g. by combining laparoscopy with percutaneous ablation needle placement.

Ninety days after the procedure, the patient chart will be evaluated to register patient characteristics and outcomes. Moreover, at one month all patients will receive a CT-scan to evaluate success rate (complete ablation response). The CT-scan is part of standard of care, it is assessed by an experienced radiologist, and it is not part of this study. Before surgery and one month after, health related quality of life (HRQoL), the psychological burden and level of recovery will be assessed. Open ablation is standard of care. Thus, the intervention group will receive a treatment with assumed fewer complications and similar success rate.

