### Secondary outcomes

- Success rate of the procedure is described as rate of complete ablations one month after procedure. A complete ablation response is defined as complete absence of enhancing tissue at the tumor site after one month on CT-scan.
- Complications reported as Comprehensive Complication Index (CCI). CCI is a scoring system for overall morbidity and is reflected on a scale from 0 (no complication) to 100 (death). It is based on Clavien-Dindo classification and takes all complications after a procedure into account.
- Highest complication grade according to the Clavien-Dindo Classification
- Wound infections within 30 days is defined as wound dehiscence requiring secondary suturing or treated conservatively. Fascial dehiscence will be recorded separately.

- Postoperative liver failure is defined by the “50-50 criteria” (prothrombin time <50% and serum bilirubin >50 µmol/L on postoperative day five).
- Postoperative pain will be assessed by Visual Analogue Scale for acute and chronic pain, pre-operatively and on each post-operative day until discharge, after seven days, 14 days and one month.
- Overall and disease-free survival.
- Procedure related mortality within 90 days.
- HRQoL before and one month after the procedure will be assessed using the Danish version of The European Organization for Research and Treatment of Cancer Quality of Life (EORTC QLQ C30) and a disease specific form for patients with HCC (QLQ HCC18), cholangio carcinoma (QLQ BIL21) or colorectal liver metastases (QLQ LM21). Depression and anxiety will be assessed before and one month after procedure using PHQ-9 and GAD-7, respectively. Recovery will be assessed with the Quality of recovery (QoR-15) before and seven days after the procedure.
- Length of hospital stay defined as time in days from operation to discharge.
- Blood loss during surgery
- Need for perioperative blood transfusion
- Conversion rate in the laparoscopic group
- Duration of procedure
- Model for Endstage Liver Disease (MELD) and Child-Pugh score before operation and on postoperative day five.
- Patients experiences of undergoing ablation will be explored by individual interviews one months after the procedure.

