##### Sample size

Based on a previous study from our center, the primary outcome (any complication Grade 2 or above, Clavien-Dindo Classification) occurred in 45% of patients undergoing open ablation. The similar complication rate from another external study was 39.5%. The hypothesis is that with a laparoscopic approach, the complication rate can be reduced to 10%. With an alpha of 5% and power of 80%, we will need 60 patients (30 in each arm).

The rate of complete ablation in one month is approximately 95% for open ablations. Using a non-inferior approach and assuming a similar rate of complete ablation in the laparoscopic group, we will need 54 patients (non-inferiority limit 15%, alpha 5% and power 80%).

By including 80 patients, both above sample-size calculations will be covered, and we will have sufficient material compensate for possible excluded patients. Before randomization, we will perform training of laparoscopic ablation using a training fantom developed for the purpose. Accuracy of laparoscopic needle placement with ultrasonography will be assessed using a gel with artificial tumors and an artificial abdominal wall. In addition, we will perform 20 cases with laparoscopic ablation to ensure that technique and learning curve is sufficient compared with our standard of care (open ablation). At this point, sufficient safety and efficacy (comparable to the literature) will be

ensured prior to randomization and additional cases and additional training may be performed is necessary.

After randomization of the first 15 laparoscopic cases, we will perform an interim analysis looking only at conversion rates in the laparoscopic group due to lack of feasibility. In case of a conversion rate above 20%, sample size will be increased according to the conversion rate, e.g. 20% more patients in each group with a conversion rate of 20%. This is done to ensure sufficient power in our comparison between the open and laparoscopic technique.

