## 5. Patients

Inclusion criteria: one or more tumors not amenable to percutaneous ablation, age > 18 years, signed informed consent, diagnosis of primary liver cancer or liver metastases from any primary tumor, and tumor suitable for ablation as primary treatment

Exclusion criteria: ablation performed in conjunction with resection, patients who cannot cooperate with the study, and patients who do not understand or speak Danish

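### At the plan's own rates about four ablation failures are expected, too few for an open-ended multivariable risk-factor model

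*Combined protocol and SAP*

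**What the plan says.** Section 4 (Statistical considerations) plans the analysis in one sentence: "To determine risk factors affecting ablation response, logistic regressions will be used in both univariable and multivariable analyses". It does not name the covariates, cap their number, give a selection rule, specify an estimation method for sparse data, or call the analysis exploratory. Section 8 lists many patient characteristics to be collected but does not tie them to this model.

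The outcome is defined under Secondary outcomes: "A complete ablation response is defined as complete absence of enhancing tissue at the tumor site after one month on CT-scan". The inclusion criteria in section 5 admit patients with "one or more tumors not amenable to percutaneous ablation".

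The expected rate comes from the Sample size section: "The rate of complete ablation in one month is approximately 95% for open ablations", and the non-inferiority calculation proceeds by "assuming a similar rate of complete ablation in the laparoscopic group". The Background gives a wider literature range: "Previous studies reported a complete ablation achieved in 94-100% of patients treated with ablation". On size, section 3 states: "We plan to include 80 patients with 40 patients per arm".

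The Aims include a comparison of the arms on this outcome ("Investigate differences in success rate (complete ablation response) between laparoscopic and open ablation"). A search for risk factors is neither an aim nor a listed outcome.

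**The concern.** In a logistic model for a binary outcome, the information is governed by the rarer outcome, here incomplete ablation. If nearly every patient has a complete response, 80 patients carry very little information about what predicts failure, however many characteristics are recorded. An unrestricted multivariable model on a handful of events gives odds ratios that are very imprecise and sometimes not finite. Those that pass p < 0.05 tend to be the overestimates. The plan's stated purpose is to establish risk factors, and it commits to publishing results. Readers could therefore take an exaggerated odds ratio, or the absence of a significant one, as informative about which patients fail ablation.

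**Working it through.** **Inputs.** 80 patients, 40 per arm (section 3). Complete ablation 95% for open and similar for laparoscopic; margin 15 points, alpha 5%, power 80% (Sample size). Literature range 94-100% (Background).

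**The plan's own figure.** Non-inferiority size per arm = (1.645 + 0.842)² x 2 x 0.95 x 0.05 / 0.15² = 26.1, rounded up to 27, so 54 in total. This matches the stated 54, using one-sided 5%. A 95% rate in both arms is therefore the plan's working assumption.

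**Expected failures.** 40 x 0.05 + 40 x 0.05 = 4.
- Binomial(80, 0.05): 2.5% and 97.5% quantiles 1 and 8; P(none) = 0.95^80 = 1.7%; P(10 or more) = 0.65%.
- Over the cited 94-100%: 80 x 0.06 = 4.8 down to 0.
- With the plan's example of a 20% increase, to 96 patients: 96 x 0.05 = 4.8.

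**Events per variable.** 4/2 = 2 with two covariates, 4/3 = 1.3 with three, 4/4 = 1 with four.

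**Chance of no finite maximum-likelihood estimate (exact).**
- Treatment alone: at least one arm has no failures. 1 - (1 - 0.95^40)² = 1 - (1 - 0.1285)² = 24.0%.
- One binary covariate at 30% prevalence (assumption), treatment not in the model: all failures fall in one level, or there are none. The per-patient chance of not being a failure with the factor is 1 - 0.30 x 0.05 = 0.985; of not being a failure without it, 1 - 0.70 x 0.05 = 0.965. So 0.985^80 + 0.965^80 - 0.95^80 = 0.298 + 0.058 - 0.017 = 34.0%.
- The figure depends strongly on covariate type. In simulation, two continuous covariates without treatment gave about 2%; four binary covariates at 30% plus treatment gave about 69%.

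**Precision and detection (simulation at 5% overall failure; covariate types and prevalences are assumptions).**
- In finite fits with one 30% binary and one continuous covariate, the median ratio of upper to lower 95% limit for the binary odds ratio was about 95. With two continuous covariates it was about 9, per standard deviation (SD).
- Detection at p < 0.05:

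| Risk factor | True odds ratio | Wald | Firth |
|---|---|---|---|
| Binary, 30% | 3 | 7-10% | 17-18% |
| Binary, 30% | 5 | 12-16% | 31-32% |
| Continuous, per SD, alone | 2 | 20% | 24% |
| Continuous, per SD, alone | 3 | 41% | 48% |
| Continuous, per SD, alone | 5 | 61% | 70% |

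- Exaggeration: a true odds ratio of 2 per SD, when significant, was estimated at a median of about 3.7 alone and about 4.7 to 4.9 with three to six further covariates. These are approximate Monte Carlo values.
- False positives in univariable runs with no true effect: 0.6-3% (Wald) and 2.5-4.5% (Firth), so not above the nominal 5%.

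**A check that needs no model.** If all four failures fell on one side of a 40/40 split, two-sided Fisher p = 2 x C(40,4)/C(80,4) = 2 x 91,390/1,581,580 = 0.116.

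**The case against.** **Failures may be commoner than planned.** At an assumed 85% laparoscopic success, 40 x 0.05 + 40 x 0.15 = 8 failures are expected (95% range 3 to 13). At the non-inferiority limit of 80%, 40 x 0.05 + 40 x 0.20 = 10. The problem eases, but these counts still do not support a model with no limit on covariates, and neither is the rate the plan assumes.

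**The method is not fixed as maximum likelihood.** Firth and exact methods are also logistic regression and are available in R, so the separation percentages apply only if ordinary fitting is used. That is correct. The low information content remains under any method.

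**Real effects can be found, and reported ones need not be false.** A reader might infer that nearly every true risk factor would be missed and that anything reported would be spurious. The calculations do not support that. A strong continuous factor, examined alone, is detected in well over half of trials, and false positives were not inflated. What stands is imprecision, poor detection of binary or moderate factors, and exaggeration of significant estimates.

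**The unit of analysis is largely settled.** A reader might infer that the plan leaves patient or tumour wholly open. The Background and Sample size sections count patients, and the success rate is described per procedure. The remaining gap is how a patient with several tumours is classified, given a definition at the tumour site. With an assumed one to two tumours per patient and 5% failure per tumour, a tumour-level model would have 4 to 8 failures before any allowance for clustering.

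**Conclusion.** The point holds and is minor. The count of about four failures follows directly from the plan's sample size and assumed rates. Nothing in the document limits the multivariable model to what four failures can carry. The separation, precision and detection figures rest on assumed covariate types and prevalences and show the scale only; the conclusion does not depend on any one of them.

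A reader might go further and infer that the trial's main results are at risk. They are not. The primary complication comparison, the Fisher tests on secondary outcomes and both sample-size calculations make no use of this regression.

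**What to change.** In section 4:
- Label the risk-factor analysis exploratory.
- Replace the open-ended multivariable model with Firth-penalised logistic regression (profile-likelihood intervals) or exact logistic regression, either univariable or with at most one or two covariates named in advance.
- State that if very few failures occur they will be listed and described instead of modelled. No particular minimum is required. A threshold of six, for example, comes from a 40/40 split (six of six failures on one side gives Fisher p = 0.026, five of five gives 0.055). It would bar a result such as four of four failures in a 24-patient subgroup of 80, where p = 0.0067.
- State how a patient with several tumours is classified and, if tumours are analysed, account for clustering within patient.

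The cost is wording only: no change to patients, visits, sample size or the primary analysis. A fully adjusted model is given up, and intervals remain wide because penalisation keeps estimates finite but adds no information.

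### Quality of life and mean VAS are compared without the pre-operative scores already collected, and mean VAS has no stated averaging window

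*Combined protocol and SAP*

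**What the plan says.** Section 4 (Statistical considerations) gives each outcome one sentence on testing. For quality of life: "Mann-Whitney U-test will be used to assess differences in the summary scores". For pain: "Mean VAS score will be compared using Mann-Whitney U-test". It mentions no covariate, change score or time point, and does not say which ratings form the mean. The general sentence on description allows "means or medians for continuous variables".

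The Secondary outcomes section shows what is collected. For quality of life: "HRQoL before and one month after the procedure will be assessed using the Danish version", with PHQ-9 and GAD-7 at the same two times. VAS is rated "pre-operatively and on each post-operative day until discharge, after seven days, 14 days and one month". Length of stay is a separate secondary outcome: "Length of hospital stay defined as time in days from operation to discharge".

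Section 4 names no test for PHQ-9, GAD-7 or QoR-15. QoR-15 timing also differs between sections. Secondary outcomes says "Recovery will be assessed with the Quality of recovery (QoR-15) before and seven days after the procedure", while section 3 (Method) says "Before surgery and one month after, health related quality of life (HRQoL), the psychological burden and level of recovery will be assessed".

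**The concern.** There are two separate issues.

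**Unused baseline.** Quality of life is one of the three aims in section 2. With about 80 patients, a pre-operative score that correlates with the one-month score removes part of the between-patient variation at no extra cost. An unadjusted rank test leaves that precision unused.

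**Undefined mean VAS.** Daily ratings stop at discharge. If a patient's mean is taken over in-hospital days, the number of days averaged is fixed after randomization by length of stay, which the trial expects may differ between arms. Pain falls after surgery, so a shorter window holds the more painful days, and the arm that goes home earlier can look worse with no difference in pain. Section 6 assumes less pain after laparoscopy, so the comparison bears on the trial's rationale. Leaving the definition open also allows it to be chosen after the data are seen.

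**Working it through.** **The plan's own figures.** The documents give no power or precision figure for quality of life or VAS. The two stated sample sizes concern complications and complete ablation. Both reproduce: 30 per arm for 45% against 10% (two-sided 5%, 80% power, continuity-corrected), and 27 per arm for 95% in both arms with a 15-point limit (one-sided 5%). Nothing below depends on an error there.

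**Quality of life: inputs.** 40 per arm (section 3). Assumed, because the documents give none: a 0.5 SD difference and a correlation r between pre-operative and one-month score of 0.3, 0.5 or 0.7.

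*Detectable difference, 80% power, two-sided 5%:*
- Unadjusted t-test: (1.960 + 0.842) × √(2/40) = 0.626 SD.
- Mann-Whitney, normal data: 0.626 / √(3/π) = 0.641 SD.
- ANCOVA: 0.626 × √(1 − r²) = 0.60, 0.54 and 0.45 SD.
- Mann-Whitney on change scores: 0.641 × √(2(1 − r)) = 0.76, 0.64 and 0.50 SD.

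*Simulated power at 0.5 SD, normal scores* (thousands of trials per cell; ranges cover separate runs):

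| Analysis | r = 0.3 | r = 0.5 | r = 0.7 |
|---|---|---|---|
| Mann-Whitney, 40 per arm | 57–59% | 57–59% | 57–59% |
| Rank ANCOVA, 40 per arm | 61–62% | 69–70% | 83–85% |
| ANCOVA, 40 per arm | 62–65% | 72–73% | 86–88% |
| Mann-Whitney, 32 per arm (20% missing) | 48–49% | 48–49% | 48–49% |
| ANCOVA, 32 per arm | 54% | 62% | 78% |

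An unadjusted t-test at 40 per arm already has about 60% power. About 2 points of the ANCOVA gain at r = 0.3 therefore come from changing the test, not from the baseline score. Adding centre changes power by 0–1 point.

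*Strongly skewed, PHQ-9-like scale (assumed distribution):* Mann-Whitney 57–58%, ordinary ANCOVA 53/59/73%, rank ANCOVA 60/67/82%. Ordinary ANCOVA loses at r = 0.3; rank ANCOVA does not.

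**VAS: inputs.** The rating schedule comes from Secondary outcomes. Assumed: the same pain curve in both arms, 50 × (1 − d)^(k − 1) mm on day k, with d = 0.10, 0.15 or 0.20; discharge after day 2 against 3, 4 or 5, or day 3 against 4 or 5.

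*Worked case, d = 0.15, day 2 against day 4.* Days 1–4 are 50.0, 42.5, 36.1 and 30.7 mm; days 7, 14 and 30 are 18.9, 6.0 and 0.4 mm.
- In-hospital days only: (50.0 + 42.5)/2 = 46.2; (50.0 + 42.5 + 36.1 + 30.7)/4 = 39.8. The earlier-discharged arm looks 6.4 mm worse.
- All post-operative ratings: (92.5 + 25.3)/5 = 23.6; (159.3 + 25.3)/7 = 26.4. The earlier-discharged arm looks 2.8 mm better.

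*All combinations:* in-hospital only, 2.2 mm (d = 0.10, day 3 against 4) to 11.4 mm (d = 0.20, day 2 against 5) worse. All ratings, 0 to 3.5 mm better.

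*True 20% benefit for the earlier-discharged arm, d = 0.15:*
- In-hospital only: 0.8 × 46.2 = 37.0 against 39.8, so 2.8 mm for day 2 against 4. For day 2 against 5 it is 37.0 against 37.1, so 0.1 mm.
- All ratings: 0.8 × 23.6 = 18.9 against 26.4, so 7.5 mm for day 2 against 4. Of this, 2.8 mm comes from the window.

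**The case against.** Mann-Whitney on one-month quality of life is a valid randomized comparison, and the plan sets no power target for it. Section 4 is silent on baseline rather than excluding it. All of this stands. A reader might infer that the quality-of-life test is biased, or that the trial is underpowered for this outcome; the documents support neither. Adjustment is an efficiency gain whose size depends on a correlation they do not give. Reading the summary-score sentence as change scores would not rescue it: nothing says so, and change scores do worse than follow-up alone when r is below 0.5.

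On VAS, a reader might infer that the planned analysis will hide a laparoscopic pain benefit or often produce a false difference. That needs an in-hospital-only mean, which the plan never states. The schedule includes seven days, 14 days and one month, and averaging all ratings leaves the benefit visible. A separate simulation with identical pain and a different assumed curve points the same way. For mean stays of 2 against 4 and 3 against 5 days, false rejection was 67% and 51% with in-hospital days only, but about 7% and 5% with all ratings.

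Mean VAS could also signify arm means at each time. The fixed later times are then sound, but later in-hospital days compare only patients still admitted. What remains is that these readings behave differently, even in sign, and the plan does not choose.

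**Conclusion.** The point holds as a worthwhile improvement to secondary analyses. The primary analysis and sample size are untouched.

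- **Quality of life:** no bias, only lost precision. Against 57–59% power unadjusted, adjustment gains a few points at r = 0.3, roughly 10–15 at 0.5 and 25–30 at 0.7. This rests on the assumed 0.5 SD effect, correlations and distributions.
- **VAS:** the definition is missing. Bias is material only if in-hospital days alone are averaged (2.2–11.4 mm) and small if all ratings are averaged (0–3.5 mm). Pain curves and stays are assumed. The mechanism needs only falling pain and unequal stays.
- **PHQ-9, GAD-7 and QoR-15:** the unnamed tests and the QoR-15 timing conflict are missing detail and wording. They are worth settling in the same edit but would not carry the point alone.

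**What to change.** In section 4, before any comparison by arm:

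1. Analyse the one-month QLQ-C30 summary score by ANCOVA on the pre-operative score and centre (the stratification factor). Report the adjusted difference with 95% CI. Keep Mann-Whitney as a fixed sensitivity analysis, with no switch of method based on residuals.
2. Analyse one-month PHQ-9 and GAD-7 by rank ANCOVA on the same covariates, fixed in advance. Describe the arms by medians, and do not present an unadjusted interval as if it matched the adjusted test.
3. Replace mean VAS with comparisons at post-operative day 1, day 7, day 14 and one month, adjusted for pre-operative VAS and centre by a named method. Name one time as the main VAS comparison. Report later in-hospital days descriptively, with the number rated. Day 1 assumes that nearly all patients are still rated then; the documents give no stays, so show the number rated there too.
4. Separately, reconcile the QoR-15 timing between section 3 and Secondary outcomes, and name its test.

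The cost is a few sentences. Every variable is already scheduled for collection, and the planned software suffices. The downside is slightly more analysis work and a linearity assumption for the summary score, against which the Mann-Whitney sensitivity analysis is a check.
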